Hypothesis: Adults with anaemia in the immediate postoperative period following major abdominal surgery have a poorer quality of recovery and higher risk of complications, leading to poor disability-free survival when compared with patients without postoperative anaemia.

BACKGROUND

More than 310 million people undergo major surgery each year around the world,¹ for which intravenous (IV) fluid therapy is routine. Although restricting IV fluids to achieve zero balance has been recommended,^{2,4} the RELIEF trial could not identify any outcome benefits using this approach in patients undergoing major abdominal surgery.⁵ In fact, a moderately liberal IV fluid regimen led to better quality of recovery and reduced the risk of acute kidney injury.⁵ Nevertheless, excess intravascular fluid volume may induce a dilutional anaemia.⁶⁻⁸ This, therefore, opens up the possibility that a diagnosis of perioperative anaemia based only on haemoglobin (Hb) concentration may be misleading – that is, when actual red cell mass is within the normal range.^{6,9} Traditional perioperative IV fluid regimens in abdominal surgery can lead to patients receiving 3 to 7 litres of fluid on the day of surgery and more than 3 litres per day for the following 3 to 4 days, leading to a 3- to 6-kg weight gain.^{10,11} This complicates the diagnosis of anaemia and evaluation of its relationship with patient outcomes.

Both preoperative anaemia and red cell transfusion are independent risk factors in major surgery.¹²⁻¹⁴ IV iron therapy is effective in treating anaemia in medical (heart failure, kidney disease), post-partum, and *preoperative* settings (orthopaedic surgery, colon cancer resection, hysterectomy, hip/knee joint replacement).¹⁵⁻¹⁹ Patient blood management (PBM) describes a patient-specific, multidisciplinary, multimodal team approach to optimising, conserving and managing the patient's own blood.²⁰ PBM aims to reduce the need for blood transfusion in an effort to improve patient outcomes.^{21,22} Australian PBM guidelines for the surgical patient are available,²³ but there is no specific PBM guidance on the treatment of *postoperative* anaemia.²⁴

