The consequences of *postoperative* anaemia remain unclear.^{22,24,25} Data from the POISE-2 trial found that postoperative anaemia was associated with an increased risk of myocardial infarction after surgery.²⁶ Postoperative anaemia is more likely if there is pre-existing anaemia, but also increased perioperative blood loss, frequent blood sampling, excess IV fluids (leading to haemodilution), sepsis, and inadequate nutritional intake after surgery.²⁴ A nadir in Hb concentration is most often observed within the first 3–4 days after surgery.²⁴ Postoperative anaemia is believed to have deleterious effects on patient outcomes, including prolonged hospital stay, increased postoperative complications, and perhaps poor survival,²² but there is very little data to support this belief.²⁵

A recent consensus statement suggested that all patients recovering from major surgery (defined as blood loss > 500 ml or lasting > 2 h) and either had preoperative anaemia or moderate-to-severe blood loss during surgery must be screened for anaemia after surgery.²⁴ Furthermore, this consensus group recommended that patients recovering from uncomplicated major surgery should have their Hb concentration measured for at least 3 days after surgery to detect anaemia.²⁴ As outlined above, this is problematic if there is fluid retention.

The role of IV iron for the treatment of postoperative anemia is unclear, with the most recent systematic review concluding that neither oral nor IV iron had a significant effect on patient quality of life or functional outcomes following surgery.²⁵ A diagnosis of iron deficiency is very difficult in the postoperative period because the acute phase inflammatory response results in spuriously elevated ferritin levels,²⁷ and several

studies have demonstrated oral iron therapy is ineffective in this setting.²⁴ However, efficacy as defined by a Hb response has been seen with IV iron.^{25,28} More recently, secondary findings in the PREVENTT study showed association between the use of IV iron and correction of postoperative anaemia (Hb response) and reduced hospital readmission for complications.

We therefore propose a study to investigate the incidence, extent, and outcomes of patients with anaemia after major surgery, including an assessment of the amount of IV fluids administered in the immediate perioperative period. ≥

STUDY DESIGN

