12. Hospital re-admission at 3, 6 and 12 months.

Fluid Therapy and Blood Transfusion: General Guidelines

Excessive fluid resuscitation can cause haemodilution⁷ and dilutional coagulopathy, and this may increase the need for red cell and other blood transfusion.⁸ All patients had the same red cell transfusion threshold of 70 g/L, but this could be modified after assessment of cardiovascular risk^{36,37} or concern for active bleeding.

Randomised group assignment

RELIEF was a large, randomized, parallel-group, controlled trial⁵. After stratification by centre and planned ICU/HDU admission (or not), patients were randomly assigned from a computer-generated list (1:1) to either a Restrictive or Liberal fluid Group. In brief, Liberal protocol group received a bolus of Hartmann's balanced salt crystalloid 10 ml/kg at the commencement of surgery followed by 8 ml/kg/h administered until the end of surgery, and then maintenance infusion continued at 1.5 ml/kg/h for at least 24 hours. Patients assigned to the Restrictive protocol group received approximately half of this IV fluid volume.⁵

Patients were blinded to Group allocation. Anaesthetists, surgeons, and intensivists had variable knowledge of Group identity. Research staff conducting all follow-ups were blinded to Group allocation.

Web-based data entry

Following completion of the paper-based CRF, data were entered by research staff to the database through a web-based data entry system. We audited the timeliness of data entry and reports were generated by the data quality committee regularly. We maximised data quality and protocol standardization by arranging start-up meetings at local scientific meetings or live streamed web based sessions, and provided regular feedback to each centre via phone and the trial web-site, along with a monthly newsletter. A complete procedures manual was produced. All study personnel had 24-h access to the study coordinating centre to resolve any questions that arose.

Adverse Event reporting was mandated.

Bias Control

RELIEF was a large trial, randomised trial. This retrospective cohort study is using all data collected during the RELIEF trial, as outlined above. All outcome data were collected by research staff blinded to Group allocation. All outcomes were clearly defined in the protocol, and most required source documentation and confirmation by blinded assessors in the endpoint adjudication committee.

STATISTICAL ANALYSIS

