All statistical analysis will be done by [name] (biostatistician). Our initial sample size calculation was based primarily on our own data and other published studies.^{38,39} This resulted in a final sample size of 3,000 that provided 80% power for the trial.⁵ We plan to analyse the intention-to-treat population of the RELIEF trial.⁵

Descriptive statistics will be used to compare the baseline characteristics of patients with and without post-operative anaemia on Day 3, hereafter titled 'anaemia groups'. The binary primary outcome, persistent disability or death to 90 days, will be compared between anaemia groups using log-binomial regression to estimate risk ratios and 95% confidence intervals directly, adjusting for RELIEF randomised group, age, sex, ASA physical status, Charlson score, preoperative aspirin, haemoglobin, type of surgery, planned HDU/ICU (either), and duration of surgery. Further possible confounders will be determined prior to commencement of the statistical analysis. Should the log-binomial model fail to converge, modified Poisson regression with robust standard errors will be used. Other binary endpoints will be analysed similarly. Duration of stay outcomes will be summarised using medians and interquartiles ranges, and compared across anaemia groups using accelerated failure time models with adjustment for the same factors. QoR-15 scores will be summarised using medians and interquartiles ranges, and compared across anaemia groups using median regression.

To assess the secondary aim, the risk of postoperative anaemia at Day 3 will be compared between RELIEF randomised arms using proportions and analysis using (unadjusted) log binomial regression.

Baseline and pre-Day 3 characteristics of patients missing the Day 3 anaemia assessment will be compared with those who have the measurement present. If there is evidence of missing Day 3 anaemia being dependent on these characteristics then multiple imputation of Day 3 anaemia will be performed using chained equations, including baseline and post-baseline variables, including the relevant outcome variables in the imputation models.

Exploratory subgroup analyses will be done for persistent disability or death to 90 days, acute kidney injury, Day 3 QoR-15, and hospital stay according to (i) RELIEF randomised group, (ii) the presence of preoperative anaemia, and (iii) receipt of a red cell transfusion. These will be reported as a web-supplement.

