IV fluids (total volume) will be tabulated according to reporting in the RELIEF trial, for intraoperative plus recovery room (combined), and Days 1, 2 and 3.

Daily weight and CRP (if done) on Day 3 will be reported as mean (SD).

STATISTICAL ANALYSES

All statistical analysis will be performed with the intention-to-treat population of the RELIEF trial.⁵

Descriptive statistics will be used to compare the baseline and pre-Day 3 characteristics of patients with and without post-operative anaemia on Day 3, hereafter titled 'anaemia groups'.

The binary primary outcome, persistent disability or death to 90 days, will be compared between anaemia groups using log-binomial regression to estimate risk ratios and 95% confidence intervals directly, adjusting for RELIEF randomised group, age, sex, ASA physical status, Charlson score, preoperative aspirin, haemoglobin (baseline), type of surgery, planned HDU/ICU (either), and duration of surgery. Should the log-binomial model fail to converge, modified Poisson regression with robust standard errors will be used. Methods for addressing missing Day 3 anaemia are provided below.

Other binary endpoints (#1-8, 12) will be analysed similarly. Duration of stay outcomes (#9,10) will be summarised using medians and interquartiles ranges, and compared across anaemia groups using parametric accelerated failure time models with adjustment for the same factors. QoR-15 scores (#11) will be summarised using medians and interquartiles ranges, and compared across anaemia groups using median regression with robust standard errors.

To assess the secondary aim, the risk of postoperative anaemia at Day 3 will be compared between RELIEF randomised arms using proportions and analysis using log binomial regression adjusted for planned ICU/HDU admission.

Baseline and pre-Day 3 characteristics of patients missing the Day 3 anaemia assessment will be compared with those who have the measurement present. If there is evidence of missing Day 3 anaemia being dependent on these characteristics then multiple imputation of Day 3 anaemia will be performed using chained equations, including baseline and post-baseline variables predictive of either Day 3 anaemia being missing or of Day 3 anaemia itself (defined by correlation ≥ 0.30 for either), including the relevant outcome variables in the imputation models.

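### Weight is to be reported as a raw mean (SD) with no preoperative reference, so the only planned measure of fluid retention does not measure retention

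*SAP*

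**What the plan says.** The SAP gives weight one sentence, under Process Data Calculations: "Daily weight and CRP (if done) on Day 3 will be reported as mean (SD"). It specifies no reference weight, change score, comparison groups or model. The sentence before it deals with fluid given: "IV fluids (total volume) will be tabulated according to reporting in the RELIEF trial", by period up to Day 3. Neither document plans a fluid balance or an output measure, so weight is the only planned quantity that could reflect fluid retained.

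The protocol's Background describes retention as a change within the patient. It cites traditional regimens as "leading to a 3- to 6-kg weight gain" and continues: "This complicates the diagnosis of anaemia and evaluation of its relationship with patient outcomes". On postoperative haemoglobin monitoring it adds: "As outlined above, this is problematic if there is fluid retention". Both documents name haemodilution in the secondary aim.

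Neither document lists preoperative weight as a recorded variable. It is implied by the BMI inclusion criteria and by weight-based dosing in the protocol's section on randomised group assignment ("crystalloid 10 ml/kg at the commencement of surgery followed by 8 ml/kg/h").

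**The concern.** Retention is the difference between a patient's weight after surgery and the same patient's weight before it. A mean of postoperative weights does not contain that difference, and its spread is mainly differences in body size.

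At stake is how a haemodilution result is interpreted. If liberal fluid is followed by more Day 3 anaemia, weight gain by arm would be direct supporting evidence of retained fluid. With raw weight, a modest real difference in retention could pass for no difference. Between anaemia groups, a difference in build could be taken for fluid, or could hide it.

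**Working it through.** **Inputs from the documents.** The protocol gives the RELIEF sample size: "This resulted in a final sample size of 3,000 that provided 80% power for the trial". Allocation was 1:1 (protocol, Randomised group assignment), so 3,000 / 2 = 1,500 per arm. The 80% power cannot be reproduced, because no event rates, effect size or alpha are given, and it does not concern weight. Only the number of patients is used here. The documents state no figure for the weight summary.

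**Assumptions, none in the documents.** SD of body weight 15 to 25 kg; correlation between preoperative and Day 3 weight 0.95 to 0.99; equal SD on both occasions; two-sided alpha 0.05; normal approximation.

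**Raw weight between arms, all 3,000 weighed.** SE = SD × √(2/1,500); power = Φ(d/SE − 1.96).

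| SD (kg) | SE (kg) | 95% half-width (kg) | Power, 1 kg | Power, 3 kg |
|---|---|---|---|---|
| 15 | 0.55 | 1.07 | 45% | about 100% |
| 20 | 0.73 | 1.43 | 28% | 98% |
| 25 | 0.91 | 1.79 | 19% | 91% |

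The difference detectable with 80% power is 1.5 to 2.6 kg. The documents do not say how many patients were weighed. With 1,500 weighed in total, power for 3 kg is 64-97%; with 750 it is 38-78%.

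**Change from preoperative weight.** SD of change = SD × √(2(1 − ρ)), so the variance ratio of raw to change is 1 / (2(1 − ρ)).

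- ρ = 0.95: 1 / 0.10 = 10.
- ρ = 0.98: 1 / 0.04 = 25.
- ρ = 0.99: 1 / 0.02 = 50.

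The SD of change runs from 2.1 kg (SD 15, ρ 0.99) to 7.9 kg (SD 25, ρ 0.95). With 1,500 per arm the SE is 0.08 to 0.29 kg, and the difference detectable with 80% power is 0.2 to 0.8 kg. In the least favourable combination, power for 1 kg is 93%, against 19% with raw weight. Adjusting for preoperative weight gives a variance of SD² × (1 − ρ²), which is (1 + ρ)/2, or 0.975 to 0.995, times that of change. Precision is therefore nearly the same, and chance imbalance in build is removed.

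**Between anaemia groups.** These groups are not randomised, so the issue is bias, and sample size does not cure it. As an illustration, suppose men outweigh women by 10 to 15 kg and the share of men differs by 10 to 30 percentage points between groups. Raw mean weight then shifts by 10 × 0.10 = 1.0 kg to 15 × 0.30 = 4.5 kg with no difference in fluid. The documents give no sex split by anaemia group, so this shows only what is possible.

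**The case against.** The strongest reply is that this is a descriptive row. No test, interval, grouping or model is attached to weight, and the secondary aim is tested on Day 3 anaemia by randomised arm. That stands, and it limits the point to interpretation.

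The sentence is also ambiguous. The Day 3 qualifier may belong to CRP alone, with weight given for each day, and the SAP is silent on change rather than against it. This stands in part. A series of daily postoperative weights would still lack a reference, because the intraoperative fluid comes before all of them.

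A reader could subtract a baseline mean. But the planned descriptive comparison is by anaemia group, its variables are not listed, and a difference of group means gives no SD of change. If weights are missing, it also compares different patients.

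Stronger readings are tempting, but the documents do not support them:

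- *Raw weight cannot show retention of 3 to 6 kg.* Between fully weighed arms it can, with 91-100% power for 3 kg. Moreover, the 3 to 6 kg is a gain within patients under traditional regimens, not an expected difference between groups in this study.
- *Sex-specific haemoglobin cut-offs make the anaemia groups differ in build.* They do not by themselves create a sex imbalance. A lower cut-off for women classifies fewer women as anaemic than a shared cut-off of 130 g/L would. Confounding by build is possible, but it is not shown.
- *Mean (SD) is also wrong for CRP.* The documents say nothing about its distribution, so no claim is made.

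**Conclusion.** The point holds as a minor one. The planned summary does not measure retention, and no other planned quantity does. Between anaemia groups raw weight can mix body build with fluid. Between arms it is unbiased but weak for small differences: 19-45% power for 1 kg, against at least 93% with change, when 1,500 per arm are weighed. It is adequate for a 3-kg arm difference if weights are near complete, and less so if they are not. A variance reduction of about 10- to 50-fold is a fair expectation.

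All of this rests on the assumed SDs and correlations and on the unknown completeness of weighing. The 1-kg difference is a benchmark chosen here; the documents name no expected arm difference. No endpoint, planned model or primary conclusion is affected.

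**What to change.** First, the sponsor should confirm that preoperative weight was recorded and state on which days weight was measured. Then replace the weight part of the SAP sentence with wording such as:

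*Weight will be reported as change from preoperative weight (kg) at Day 3, as mean (SD), by randomised arm and by anaemia group, in patients with both values, giving the number with both. The difference between arms will be given with a 95% CI, adjusted for preoperative weight, as supportive description only.*

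The adjusted arm difference is a small addition to what the SAP plans, which is why it should be labelled supportive. No interval is proposed between anaemia groups, where even change in weight remains a non-randomised comparison.

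The cost is one derived variable and the loss, from this row only, of patients missing either weight. If many are missing, the reported count will show it.

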A cohort study comparing patients with and without postoperative anaemia, using prospective data collected in a large, pragmatic, multicentre, randomized trial, the RELIEF trial, in which patients were randomly assigned to either a restrictive (zero balance) or liberal IV fluid regimen, stratified by site and planned HDU/ICU admission.⁵ The intention-to-treat population of the RELIEF trial will be utilised, namely all participants who were enrolled, randomised and underwent induction of general anaesthesia for eligible surgery.

Inclusion and exclusion criteria are as for the RELIEF trial.⁵

GROUP AND ENDPOINT DEFINITIONS

ANAEMIA GROUP DEFINITION

Postoperative anaemia will be defined according to the World Health Organisation definition (males Hb <130 g/L, and female Hb <120 g/L), as measured on postoperative Day 3, using the “Lowest Haemoglobin concentration”. Patients with missing Day 3 haemoglobin data will have these values imputed rather than these patients being excluded (details below).

A secondary group definition will be studied defined as patients with severe anaemia (Hb <100 g/L) at day 3 postoperatively.

LIBERAL PERIOPERATIVE IV FLUID GROUP DEFINITION

Liberal and restrictive perioperative IV fluid groups are defined as the corresponding randomised arms of the RELIEF trial. In brief, Liberal protocol group received a bolus of Hartmann’s balanced salt crystalloid 10 ml/kg at the commencement of surgery followed by 8 ml/kg/h administered until the end of surgery, and then maintenance infusion continued at 1.5 ml/kg/h for at least 24 hours. Patients assigned to the Restrictive protocol group received approximately half of this IV fluid volume.⁵

ENDPOINT DEFINITIONS

Primary endpoint

Persistent disability or death by 90 days, where persistent disability was defined as a WHODAS 2.0 score of at least 24 points (on the 48-point scale) at both 30 days and 90 days post-operatively,³¹ reflecting a disability level of at least 25% and being the threshold point between “disabled” and

“not disabled” as per WHO guidelines.³³ Disability was assessed by the participant, but if unable then we used the proxy’s report.

Secondary endpoints

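### The primary anaemia model neither conditions on site nor allows for within-site correlation, so its risk ratio could be biased in either direction and its interval too narrow

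*SAP*

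**What the plan says.** The SAP (Study Design) describes a cohort drawn from a multicentre trial whose randomisation was "stratified by site and planned HDU/ICU admission". The Protocol (Randomised group assignment) agrees: "After stratification by centre and planned ICU/HDU admission (or not), patients were randomly assigned" to the two fluid groups.

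The primary model in the SAP (Statistical Analyses) is a log-binomial regression of the 90-day outcome on Day 3 anaemia, "adjusting for RELIEF randomised group, age, sex, ASA physical status, Charlson score", then aspirin use before surgery, baseline haemoglobin and the type of operation, and finally "planned HDU/ICU (either), and duration of surgery". That makes ten covariates. Planned HDU/ICU is one of them; site is not. The other binary endpoints are analysed in the same way, and the length-of-stay models reuse the same covariates.

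No random centre effect, site stratification or site-clustered variance appears. Robust standard errors are named for the modified Poisson fallback and for median regression, with no mention of clustering.

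The Protocol (Statistical Analysis) left room to add confounders before the analysis began. The later SAP does not carry that statement and names no further confounder. For the secondary aim, the SAP compares the randomised fluid arms with adjustment for planned ICU/HDU only.

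**The concern.** The exposure is an observed haemoglobin, not an allocation, so the primary result depends on how well the model handles common causes of Day 3 anaemia and of disability or death. The SAP's Background lists causes of postoperative anaemia that could plausibly vary between hospitals and also affect outcome: blood loss, blood sampling, fluid excess, sepsis and poor nutrition. Only fluid is represented in the model, through randomised group. Site comes before the exposure, so conditioning on it does not adjust away part of the anaemia effect, and it can stand in for unmeasured local practice.

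Two things are at stake. Residual centre differences in both anaemia and outcome, if correlated, would shift the risk ratio up or down. Shared within-site variation in both would make an interval that treats patients as independent too short.

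**Working it through.** **The plan's own figure.** The Protocol gives 3,000 patients and 80% power, but for the parent trial's fluid comparison. It states no event rate, effect size or alpha, so the figure cannot be reproduced, and it is not the power of the anaemia comparison. Only the 3,000 is used below. The number of sites, the ICCs and the centre-level rates are all assumptions.

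**Bias when the true RR is 1.** Take two equal site groups with outcome risks r1, r2 and anaemia proportions p1, p2, no patient covariates, and no anaemia effect within either group. The crude RR is

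[(p1·r1 + p2·r2)/(p1 + p2)] ÷ [((1−p1)·r1 + (1−p2)·r2)/(2 − p1 − p2)].

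- Higher-risk sites have more anaemia (8%, 14%; 0.60, 0.80): (0.048 + 0.112)/1.4 = 0.1143; (0.032 + 0.028)/0.6 = 0.1000; RR = 1.14.
- Higher-risk sites have less anaemia (8%, 14%; 0.80, 0.60): (0.064 + 0.084)/1.4 = 0.1057; (0.016 + 0.056)/0.6 = 0.1200; RR = 0.88.
- Equal anaemia in both groups (0.70, 0.70): both risks are 0.11; RR = 1.00.

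These values are not bounds. Anaemia of 0.65 and 0.75 with the same risks gives 0.157/1.4 ÷ 0.063/0.6 = 1.07. Risks of 6% and 16% with anaemia of 0.60 and 0.85 give 0.172/1.45 ÷ 0.048/0.55 = 1.36.

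**Precision.** For a patient-level exposure, design effect = 1 + (m − 1)·ICC(anaemia)·ICC(outcome), with m = 3000/number of sites. The standard error grows by its square root.

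| Sites (m) | ICC anaemia | ICC outcome | Design effect | SE ratio |
|---|---|---|---|---|
| any | 0 | any | 1.00 | 1.00 |
| 50 (60) | 0.05 | 0.02 | 1 + 59×0.001 = 1.059 | 1.03 |
| 50 (60) | 0.10 | 0.05 | 1 + 59×0.005 = 1.295 | 1.14 |
| 30 (100) | 0.10 | 0.05 | 1 + 99×0.005 = 1.495 | 1.22 |

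The 8%/14% and 60%/80% example itself implies smaller ICCs: outcome 0.03²/(0.11×0.89) = 0.0009/0.0979 = 0.009, and anaemia 0.10²/(0.70×0.30) = 0.048. With 30 to 50 sites these give standard errors only about 1% to 2% larger. The upper end of the precision range therefore assumes more between-site variation in outcome than the bias example does.

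**Simulation with a true RR of 1.30.** There were 300 runs per scenario, with 3,000 patients in 20 or 50 unequal centres, anaemia prevalence 75%, reference risk 14%, between-centre SD 0 to 0.7 (log odds of anaemia) and 0.2 to 0.4 (log risk of outcome), and no patient covariates.

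| Analysis | Centre anaemia and outcome levels | Mean RR | 95% CI coverage |
|---|---|---|---|
| No site, ordinary robust SE | uncorrelated | 1.29–1.31 | 90–96% |
| No site, ordinary robust SE | correlation ±0.5 | 1.16–1.49 | 71–95% |
| No site, SE clustered on site | correlation ±0.5 | 1.16–1.49 | 78–93% |
| Site-stratified Mantel-Haenszel | all scenarios | 1.30–1.32 | 92–97% |

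Clustering the standard error leaves the estimate, and so the bias, unchanged. Conditioning on site removes the bias.

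**The case against.** The strongest reply is that nothing in the documents shows centres differing in anaemia or outcome, and that much points to uniform conduct. The Protocol gives one transfusion threshold for all patients, a procedures manual, start-up meetings, blinded follow-up staff and endpoint adjudication. Type of surgery, baseline haemoglobin, ASA status, Charlson score and planned HDU/ICU may absorb much of any centre difference. This stands: a reader might infer that site does confound the anaemia effect, but the documents support only that it could.

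A reader might also take the transfusion clause, "but this could be modified after assessment of cardiovascular risk", as evidence of differing centre practice. It concerns individual patients' risk, and nothing ties it to centre. Whether a Day 3 haemoglobin was taken is covered by the SAP's separate missing-data plan.

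A third tempting reading is that site must be in the model because it was a stratification factor. Site stratified the fluid allocation, not anaemia, so that argument applies directly only to the secondary-aim comparison. For the primary aim, the reason to adjust is that site is a plausible confounder and a cluster.

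Finally, many site indicators are impractical for rare endpoints. That also stands, and it limits the fix. What the reply does not answer is that the SAP has no provision for site and no longer leaves the confounder list open.

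**Conclusion.** The omission is real and nothing else in the SAP repairs it. Its consequence is conditional: bias requires residual, correlated centre differences in Day 3 anaemia and outcome, and loss of precision depends on the product of two ICCs that the documents do not give. Under the illustrative inputs above, a null effect could appear as about 0.88 to 1.14, and true standard errors could be about 0% to 22% larger than reported with 30 to 50 sites. Both effects could be negligible. The bias figures ignore patient covariates, so adjustment could reduce them. A claim that the planned result is confounded, or biased in a known direction, would go beyond the documents. This is an inexpensive improvement to an observational analysis, and it is more credible if prespecified than if added after results are seen.

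**What to change.** In the primary model and the binary-endpoint models that reuse its covariates, condition on site. Use site indicators with very small sites pooled by a rule fixed before analysis, or a site-stratified analysis. If modified Poisson is used, cluster its robust variance on site.

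Do not rely on a plain random intercept, which assumes site effects are independent of anaemia, or on cluster-robust errors alone. Neither reliably removes confounding by site. For endpoints too rare to support many indicators, site may be handled in a sensitivity analysis.

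Separately, add site to the secondary-aim fluid-arm model alongside planned ICU/HDU, because both factors stratified that randomisation.

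The cost is a short SAP amendment using a variable already held. Small sites must be pooled, and the log-binomial model becomes more likely to fall back to the modified Poisson model already named. If Day 3 anaemia is imputed, site should also enter the imputation model so that it matches the analysis.

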Exploratory subgroup analyses will be done for persistent disability or death to 90 days, acute kidney injury, Day 3 QoR-15, and hospital stay according to (i) RELIEF randomised group, (ii) the presence of preoperative anaemia, and (iii) receipt of a red cell transfusion. These will be reported as a web-supplement.

Secondary analyses of those with and without more marked anaemia (Hb <100 g/L) will be undertaken for the primary outcome (persistent disability or death to 90 days), plus Day 3 QoR-15 score and hospital re-admissions at 3 months.

REFERENCE

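### The plan states no confounder adjustment for QoR-15, the only endpoint compared between the non-randomised anaemia groups without it, so six planned analyses would be crude if run as written

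*SAP*

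**What the plan says.** The Statistical Analyses section of the SAP describes five comparison models.

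- **Primary outcome:** log-binomial regression adjusted for ten factors: randomised group, age, sex, ASA status, Charlson score, preoperative aspirin, baseline haemoglobin, type of surgery, planned HDU/ICU and duration of surgery.
- **Other binary endpoints:** "Other binary endpoints (#1-8, 12) will be analysed similarly".
- **ICU and hospital stay (#9, 10):** "compared across anaemia groups using parametric accelerated failure time models with adjustment for the same factors".
- **QoR-15 (#11):** "compared across anaemia groups using median regression with robust standard errors".
- **Randomised arms (secondary aim):** "log binomial regression adjusted for planned ICU/HDU admission".

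In the protocol's Statistical Analysis section, QoR-15 is likewise only "compared across anaemia groups using median regression". The randomised-arm comparison there is specified "using proportions and analysis using (unadjusted) log binomial regression".

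QoR-15 is measured on Days 3 and 30. The Day 3 score also enters the exploratory subgroup analyses, which cover persistent disability or death, "acute kidney injury, Day 3 QoR-15, and hospital stay according to (i) RELIEF randomised group" and by two further factors (preoperative anaemia and red cell transfusion). It enters the Hb <100 g/L analyses as well: the primary outcome, "plus Day 3 QoR-15 score and hospital re-admissions at 3 months".

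**The concern.** Patients are not randomised to anaemia. The SAP's background says that pre-existing anaemia makes postoperative anaemia more likely, and that preoperative anaemia is an independent risk factor in major surgery. On the plan's own account, baseline haemoglobin is therefore related to both exposure and prognosis, and it is one of the ten adjustment factors for the primary outcome. Age, ASA status, comorbidity and type of surgery are plausible confounders too.

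A median regression with anaemia group as its only predictor estimates the crude difference in medians. Robust standard errors change the estimated precision of that difference; they leave the confounding in it untouched.

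Quality of recovery is the first outcome named in the hypothesis and serves the aim of studying patient-centred outcomes. A crude QoR-15 difference could not be separated from case mix, and it would be reported beside adjusted estimates for every other endpoint, with which it is not comparable. The gap also leaves an analyst free to choose between a crude and an adjusted model after seeing the data.

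**Working it through.** The check is a reading of the text and a count. The plan gives no figure of its own to reproduce on this point.

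**Step 1: covariates by model (SAP, Statistical Analyses).**

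| Model | Endpoints | Covariates |
|---|---|---|
| Log-binomial, primary | Primary | Ten, listed |
| Log-binomial, other binary | #1-8, #12 | Carried over from the primary model |
| Accelerated failure time | #9, #10 | Carried over explicitly |
| Median regression | #11 (QoR-15) | None stated or carried over |
| Log-binomial, randomised arms | Day 3 anaemia | Planned ICU/HDU admission |

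Four of the five models have a covariate set. The exception is QoR-15.

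**Step 2: endpoints compared between anaemia groups.** There are 1 primary + 12 numbered = 13. Adjustment is stated or carried over for 1 (primary) + 8 (#1-8) + 2 (#9-10) + 1 (#12) = 12. The remaining one is #11. Transfusion, IV fluid volume, weight and CRP are process data with no between-group model, so they are not counted.

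**Step 3: can the gap be filled from elsewhere?** The carry-over to other binary endpoints is limited by endpoint number and omits #11. The carry-over for the stay outcomes is attached to the accelerated failure time models. The protocol's QoR-15 sentence has no covariates either, and its provision for settling further confounders later does not mention QoR-15. No other section supplies a covariate set.

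**Step 4: planned QoR-15 analyses affected.**

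- Main analyses, Day 3 and Day 30: 2
- Day 3 by randomised group, preoperative anaemia and red cell transfusion: 3
- Day 3 under the Hb <100 g/L definition: 1

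Total: 2 + 3 + 1 = 6. With the two strata of each subgroup factor counted separately, it is 2 + 6 + 1 = 9.

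The first two come directly from the QoR-15 sentence. The other four follow only if its method is carried forward, because the subgroup and Hb <100 g/L paragraphs restate no model for any endpoint.

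**Step 5: size of the bias.** For a single confounder acting linearly, the spurious difference is roughly its imbalance between anaemia groups multiplied by its effect on QoR-15. The documents give neither quantity, nor a QoR-15 standard deviation or the prevalence of anaemia, so no figure is derived.

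**The case against.** The strongest reply is that the text is silent and does not call for a crude analysis. The protocol labels a comparison as unadjusted where it means that, and does not do so for QoR-15. The QoR-15 sentence directly follows one that adjusts, and median regression accepts covariates. Adjustment may well have been intended. This stands as an account of intent. It does not tell the analyst what to fit: two people could follow the SAP faithfully and report different QoR-15 results. The SAP also revised this very sentence, adding robust standard errors, and added a covariate to the randomised-arm model, yet still named none for QoR-15.

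A second reply is that six overstates the problem. Only two analyses come directly from the sentence, and three of the other four are exploratory results for a web supplement. That is a fair description, but the count is correct once the method is carried forward, and one missing clause causes all six.

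A third is that adjustment of the other binary endpoints rests on a single word. It does, but in context that word points to the adjusted primary model; QoR-15 has no such pointer.

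A fourth is that other planned work helps: the descriptive comparison of the anaemia groups, and the Day 3 QoR-15 subgroup analysis by preoperative anaemia. The first shows imbalance without correcting for it. The second deals in part with one of the ten factors, at one time point, as an exploratory analysis. Finally, the background ties preoperative anaemia to surgical risk in general and not to QoR-15 specifically. That is true, and it is one reason why no size of bias is claimed.

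**Conclusion.** The concern holds. QoR-15 is the one endpoint of 13 for which no adjustment is stated or carried over in the comparison of anaemia groups. Run as written, its six planned analyses (two direct, four by carrying the method forward) would be crude contrasts between non-randomised groups. The conclusion rests on a literal reading of the QoR-15 sentence and allows that the omission may be a drafting slip. The direction and size of any bias cannot be determined from the documents. The primary endpoint and endpoints #1-10 and #12 are unaffected. It should be fixed before analysis, because it concerns an outcome named in the hypothesis and the correction costs almost nothing.

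**What to change.** In the SAP's QoR-15 sentence, add that the median regression is adjusted for the same factors as the primary outcome. State that this covers Days 3 and 30, the Day 3 subgroup analyses and the Day 3 analysis for Hb <100 g/L. If the subgroup analysis by randomised group is run separately within arms, randomised group drops out of the covariate list there, since it is constant. If an unadjusted QoR-15 comparison is also wanted, label it as such and report it beside the adjusted one.

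The cost is one clause in the SAP. All ten covariates are already required for the primary model, so no new data are needed.
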